STUDY TITLE:

Pain Reduction with Intranasal Medication for Extremity Injuries (PRIME): A Randomized Clinical Noninferiority Trial of Intranasal Ketamine vs. Fentanyl

PROTOCOL TITLE:

Pain Reduction with Intranasal Medications for Extremity injuries (PRIME)

TRIAL REGISTRATION:

NCT02778880

DOCUMENT:

Study Protocol and Statistical Analysis Plan

DOCUMENT DATE:

November 26, 2018

PROTOCOL SYNOPSIS

STUDY TITLE:

A Randomized Controlled Trial of Intranasal Sub-dissociative Dosing of Ketamine Compared to Intranasal Fentanyl for Treatment of Pain Associated with Acute Extremity Injuries in Children

PROTOCOL TITLE

Pain Reduction with Intranasal Medications for Extremity injuries (PRIME)

PRINCIPAL INVESTIGATOR:

[name]
Assistant [name]
Division of Pediatric Emergency Medicine
Cincinnati Children's Hospital Medical Center
[contact]

CO-INVESTIGATORS:

[name]
[name], MSCE
[name], BCPS
[name]

I. ABSTRACT

Introduction: Inadequate pain control in the emergency department, particularly in the pediatric population, is a major health concern. The intranasal route of medication administration is gaining popularity secondary to its rapid onset of action, minimal discomfort for the patient and relative simplicity. When pediatric patients present with moderate to severe pain from traumatic injuries, opioids are currently the most frequently used class of analgesia, but they may not always be the best option for numerous reasons. Sub-dissociative dosing of ketamine has been shown to be an effective alternative to opioids in providing adequate pain relief.

Objectives: The objectives of this study are to 1) determine if intranasal ketamine is non-inferior to intranasal fentanyl in reduction of pain in children presenting with extremity injuries and 2) define and compare the level of sedation and respiratory side effect profile associated with intranasal ketamine and fentanyl.

Methods: The proposed study is a double-blind, randomized clinical non-inferiority trial of intranasal sub-dissociative ketamine compared to intranasal fentanyl for children ages 8 through 17 years of age presenting to the emergency department with moderate or severe pain due to traumatic extremity injury.

Discussion: This study will determine whether intranasal ketamine is an effective alternative to intranasal fentanyl for analgesia in children. This would be particularly useful in children who experience adverse effects with opioids, have developed opioid tolerance as a result of chronic painful conditions, have poor opioid sensitivity due to their genetic predisposition, in pediatric trauma patients with hypotension or in patients requiring procedural sedation during their emergency department visit.

II. PURPOSE OF STUDY

The purpose of this study is to compare intranasal sub-dissociative dosing of ketamine with intranasal fentanyl for acute pain associated with traumatic limb injuries in children 8-17 years of age presenting to the emergency department.

Primary Objective (or Aim)

The primary objective of this study is to determine if intranasal sub-dissociative ketamine (1.5 mg/kg) is non-inferior to intranasal fentanyl (2 mcg/kg) in reduction of moderate and severe pain (VAS score greater than 35 mm [1]) associated with extremity injuries in children ages 8 years through 17 years of age.

Hypothesis #1: Intranasal sub-dissociative ketamine (1.5 mg/kg) and intranasal fentanyl (2 mcg/kg) will both reduce pain by a mean VAS score of at least 15 mm. There will be no significant difference in the means for reduction in pain score between patients receiving intranasal ketamine and those receiving intranasal fentanyl.

Secondary Objective (or Aim)

The secondary objective is to define and compare the level of sedation associated with intranasal sub-dissociative ketamine (1.5 mg/kg) and intranasal fentanyl (2 mcg/kg) as measured by the University of Michigan Sedation Scale Score and capnometry values.

Hypothesis #2a: There will be no significant difference in mean sedation scale scores between the intranasal ketamine group and the intranasal fentanyl group.

Hypothesis #2b: There will be no significant difference in the mean capnometry values of the two groups. Patients in both groups will not experience hypopneic hypoventilation (decrease in capnometry value of ≥ 10 mm Hg).

III. BACKGROUND

A recent Institute of Medicine report illustrates that inadequate pain control is a major public health concern [2], especially in the emergency department [3]. Despite this increased awareness, pain continues to be underdiagnosed and undertreated, particularly in the pediatric population [4, 5]. In one study, less than half of 172 children presenting with acute limb fractures received an analgesic during their emergency department visit[6]. A more recent study in 2012 looking at 773 children with long bone fractures demonstrated that 10% received adequate pain medication, 31% received inadequate pain medication and 59% received no pain medication within the first hour of arriving in the emergency department [7]. In combined emergency departments where both adults and pediatric patients are treated, children are significantly less likely than adults to received pain medications [8, 9], with the youngest children being the most vulnerable population [7, 10]. Furthermore, when children do receive pain medication, they often encounter long delays in medication administration [11] possibly due to the time required to obtain intravenous access. More recently, the intranasal route has been shown to offer a more efficient alternative to allow for faster delivery of pain medication [12]. This route is gaining popularity secondary to its rapid onset of action, minimal discomfort for the patient and relative simplicity.

Opioids are the most commonly used class of analgesic pain medication for children presenting in severe pain due to traumatic injuries [7]. Their use during pediatric emergency department visits has increased significantly over the past decade [13]. However, multiple studies show the majority of children who present in severe pain do not receive opioids, receive doses that are below those recommended [4,

7-10, 14] or experience long delays in receiving opioids [11, 15]. The reasons for this are unclear, but we speculate that this may be due in part to fear of adverse effects of opioids, provider inexperience with opioid use in children or fear of contributing to opioid tolerance or abuse. Additionally, due to genetic variations that may affect opioid sensitivity, ideal dosing to adequately control severe pain in the majority of patients yet avoid adverse medication-related side effects is difficult to ascertain and may lead providers to seek out non-opioid alternatives for patients with acute severe pain [16-18].

In the adult population, low dose ketamine is well tolerated and has been used successfully as an adjuvant [19-25] and an alternative [26-30] to opioids to provide adequate, rapid pain relief in the emergency department. One study demonstrated that the majority of patients and physicians were satisfied with sub-dissociative dosing of ketamine and provided reasons why physicians opted to use ketamine, including opioid failure, concern for respiratory depression, concern for opioid allergy and concern for hypotension. In this study, 96% of emergency medicine physicians felt that low dose ketamine was underused [23]. Though most of these adult studies used the intravenous route, intranasal ketamine has also been used successfully in adults with acute pain in the emergency department, inpatient and outpatient settings [31-38].

As a dissociative anesthetic, ketamine is the most commonly used agent to facilitate painful procedures in the pediatric emergency department [39]. At lower doses, it has been used in children to provide analgesia in a variety of acute and chronic pain settings [40]. Low dose ketamine has been used effectively in children with terminal diagnoses [41-43], sickle cell disease [44], perioperative pain [45, 46], traumatic injuries [47, 48], extensive burns [49] and conditions where opioids are contraindicated [50]. As with the adult population, ketamine has been used via the intranasal route to provide adequate analgesia and sedation in children, specifically in the pre-hospital setting and in those undergoing various procedures [51-59].

To our knowledge, the PICHFORK trial was the first study to demonstrate the use of intranasal sub-dissociative dose ketamine as monotherapy for acute pain in children presenting to the emergency department with traumatic injuries [60, 61]. In this study, intranasal fentanyl and ketamine were associated with similar pain reduction and satisfaction scores. These study results have yet to be replicated. If the results are reproducible, intranasal ketamine would be particularly useful in children who experience adverse effects with opioids, have developed opioid tolerance as a result of chronic painful conditions, have poor opioid sensitivity due to their genetic predisposition or in pediatric trauma patients with hypotension. Additionally, for patients that require procedural sedation for fracture reduction, avoiding opioids early in the emergency department visit may help decrease sedation recovery time [62]. During the PICHFORK trial, adverse events were documented based on patient self-report. However, there have been no studies that document side effects, vital signs, and continuous end tidal CO₂ levels after administration of intranasal ketamine through direct observation via video monitoring. The objective of this study is to compare intranasal sub-dissociative ketamine with intranasal fentanyl for treatment of acute pain associated with traumatic limb injuries in children presenting to the emergency department and to document an objective respiratory side effect profile utilizing noninvasive capnometry. More specifically, we will compare analgesic effect, sedation level, vital signs, continuous end tidal CO₂ monitoring and adverse events.

Findings from Clinical Studies

Clinical Studies of Sub-dissociative (Low-Dose) Dose Ketamine in Adults

Intravenous (IV) Administration

When used as monotherapy, subdissociative intravenous ketamine has been shown to provide effective analgesia and safety comparable to morphine for acute pain in the emergency department [27, 28]. Galinski, et al demonstrated that low doses of IV ketamine significantly lowered consumption of morphine by patients presenting to the emergency department with severe acute pain and resulted in minimal side effects (6 % with nausea/vomiting and 36% with neuropsychological effects, such as dizziness and dysphoria, in the ketamine group vs 6% with nausea/vomiting and 3% with neuropsychological effects in the placebo group) [25]. Ketamine combined with either morphine or hydromorphone has been shown to provide analgesia superior to that of morphine alone and resulted in only few minor side effects [19-22, 24]. In the pre-hospital setting, Tran et al found that ketamine had an analgesic effect similar to morphine and carried a lower risk of vomiting and airway problems than morphine. They also discovered that ketamine tended to improve blood pressure in hypotensive patients to a greater degree [63] (increase of 9.3 mm Hg with ketamine vs 4.8 mm Hg with morphine). In adult patients requiring procedural sedation and analgesia, Messenger et al found that patients receiving fentanyl and propofol were 5.1 times more likely to have a serious intrasedation event than patients receiving ketamine and propofol but the two groups had similar analgesic efficacy [29].

Intranasal (IN) Administration

More recently, the intranasal route has been a highly effective method of administering ketamine at sub-dissociative doses. One study revealed that intranasal ketamine was an effective analgesic agent in 56% of patients presenting to the emergency department with severe pain [32] while another demonstrated clinically significant reduction in pain scores in 88% of ED patients [31]. In both studies, IN ketamine resulted in very mild, transient side effects. Intranasal ketamine has been shown to be a safe, well-tolerated alternative to opioids for moderate to severe postoperative pain in adult patients [35, 38]. Furthermore, intranasal ketamine has provided rapid onset analgesia for breakthrough pain in adult patients with chronic pain conditions [33, 34]. One study showed that patients receiving ketamine achieved pain relief within 10 minutes of dosing which lasted up to 60 minutes and none of these patients required rescue medication to treat the pain episode [34]. **(See Appendix A for further details)**

TABLE 1: Sub-dissociative Dose Intranasal Ketamine for Analgesia in Adults

Study	N	Ages	Setting	Design	Doses	Route	Outcome	Adverse Effects
Yeaman, 2014	72	26-52 years (IQR)	Emergency Department, Australia	Prospective observational study: Ketamine, second dose if no improvement in 15 min	0.7-1 mg/kg, second dose (if necessary) 0.5 mg/kg, median total dose 0.98 mg/kg	IN	56% reported VAS reduction ≥ 20 mm at 30 minutes	Dizziness 32% Euphoria 24% Unpleasant taste 22% Drowsiness 19% Nausea 12% Numbness 8% Blurred vision 5% Nasal congestion 4% Throat irritation 3% Headache 3% None 21% No serious AEs
Andolfatto, 2013	40	36-57 years (IQR)	Emergency Department, Canada	Prospective observational study: Ketamine	0.5-0.75 mg/kg	IN	88% reported VAS reduction ≥ 13 mm at 30 minutes	(All transient and did not require treatment) Dizziness 38% Unreality feeling 25% Fatigue 10% Nausea 8% Mood change 8% Hearing change 3% *No headache, general discomfort or hallucination *No serious AEs
Carr, 2004	20	≥ 18 years	Outpatient, USA	Randomized double blind crossover trial: Ketamine vs placebo	Ketamine 10-50 mg	IN	Mean reduction in NPIS (10 point scale) score was 2.65 for ketamine vs 0.81 for placebo. IN ketamine is safe and effective for break through pain	Fatigue 45% Dizziness 20% Unreality feeling 20% Vision changes 10% Nausea 10% Hearing change 5% Mood change 5% *No serious AEs *No clinically significant change in vital signs
Christensen, 2007	40	≥ 16 years	Postoperative USA	Randomized double blind single dose parallel study: Ketamine #1 vs #2 vs #3 vs placebo	Ketamine 1 10 mg Ketamine 2 30 mg Ketamine 3 50 mg	IN	IN Ketamine at 50 mg dose demonstrated statistically significant pain relief (VAS score) compared to placebo. Largest difference in mean VAS scores relative to placebo was 46.5 mm at 30 minutes.	In all 4 groups: Hypertension 20% Poor concentration 8% Throat irritation 8% Tachycardia 8% Emesis 5% Placebo vs ketamine: Placebo-headache 50% Ketamine-dizzy 58%, fatigue 55%, nausea 25%, psychomimetic effects 27% No serious AEs

Afridi, 2013	18	18-57	Inpatient and Outpatient, London	Randomized double blind parallel controlled trial: Ketamine vs Midazolam	Ketamine 25 mg Midazolam 2 mg	IN	Ketamine reduced migraine severity but not the duration of aura, whereas midazolam as no effect	Ketamine: Euphoria/unreality 55% Midazolam: Sedation/giddy 44%
--------------	----	-------	----------------------------------	--	----------------------------------	----	---	---

Clinical Studies of Sub-dissociative Dose Ketamine in Children

Intravenous (IV) Administration

Sub-dissociative intravenous dosing of ketamine has been used safely and effectively in a variety of acute and chronic pediatric conditions. One meta-analysis found that administration of ketamine was associated with decreased PACU postoperative pain intensity and analgesic requirement [45]. Two studies demonstrated that ketamine given prior to tonsillectomy resulted in significantly lower pain scores and less rescue analgesic consumption postoperatively with no difference in the incidence of vomiting or psychological sequelae [46, 64]. White et al described the use of ketamine as effective analgesia in children with toxic megacolon, a painful condition where morphine is contraindicated. None of these children reported adverse effects [50]. White et al also described the long-term (37 days), successful use of ketamine for a child with extensive burns. This patient tolerated the medication well, never developed signs of tolerance and was able to be weaned rapidly without adverse consequences [49]. Various hematologic and oncologic painful conditions that are insufficiently controlled with opioids have been effectively treated with low dose ketamine infusions. Two studies showed an opioid sparing effect of ketamine with no significant increase in adverse effects in children with cancer-related pain [41, 42], while another study described sickle cells patients with opioid-refractory pain who achieved clinically significant analgesia after the initiation of ketamine infusion [44]. Taylor et al describes the use of ketamine for end-of-life neuropathic pain in which all patients noted subjective pain relief and 79% of patients had no adverse effects [43]. Ketamine has been used effectively in the pre-hospital setting for pediatric trauma patients. None of these patients demonstrated a loss of airway, oxygen desaturation or clinically significant emergence reaction after ketamine [48]. One emergency department study demonstrated that ketamine combined with midazolam is more effective than fentanyl combined with midazolam when used for emergency pediatric orthopedic procedures and that respiratory complications occurred less frequently with ketamine than fentanyl [47].

Intranasal (IN) Administration

The intranasal route of administering ketamine to children has become more popular over the past few years. A study done in 2013 determined that 1 mg/kg intranasal ketamine provided adequate analgesia with only mild, transient side effects that did not require any treatment. None of these patients experienced dissociation or hallucination [61]. The PICHFORK trial followed in which intranasal ketamine and intranasal fentanyl were associated with similar pain reduction (82% and 79% respectively had VAS reductions > 20 mm) and satisfaction scores (83% and 72% respectively achieved satisfaction) in patients with pain from limb injuries. Again, these patients experienced no serious adverse events [60]. One case series and one case report describe the effective use of intranasal ketamine in patients where intravenous access could not be established. Patients encountered few, non-serious side effects [52, 53]. Tsze et al illustrates the use of various doses (3, 6, or 9 mg/kg) of intranasal ketamine for procedural sedation in pediatric laceration repair. The only adverse event documented was vomiting in 1 patient

[51]. Another study explored the use of ketamine in uncooperative pediatric dental patients. The overall sedation success rate was 89% with ketamine only, 84% with ketamine plus midazolam and 69% with midazolam only. There were no significant adverse effects in any of the three groups [55]. Intranasal ketamine was also found to be a safe and effective premedication in children undergoing MRI with nausea and vomiting as the only documented side effect [57]. Multiple studies have demonstrated the successful use of intranasal ketamine in combination with either intranasal midazolam or sufentanil as an analgesic or sedative for pediatric procedures [54, 56, 58, 59]. These studies demonstrated only few, mild adverse effects with intranasal ketamine. **(See Appendix B for further details)**

TABLE 2: Sub-dissociative and Dissociative Dose Intranasal Ketamine for Analgesia in Children

Study	N	Ages	Setting	Design	Doses	Route	Outcome	Adverse Effects
Graudins, 2015 Ketamine for analgesia (sub-dissociative low dose)	73	3-13 years	Emergency Department, Australia	Double blind, randomized controlled trial: Fentanyl vs Ketamine	Fentanyl 1.5 mcg/kg Ketamine 1 mg/kg	IN	Median reduction in VAS score at 30 minutes for ketamine was 45 mm and for fentanyl was 40 mm (no significant difference between groups), which was maintained to 60 minutes in both groups.	Fentanyl: Bad Taste 42% Drowsiness 21% Dizziness 17% Itchy nose 12% Nausea 4% Dysphoria 4% Hallucinations 0% Ketamine: Bad Taste 25% Drowsiness 16% Dizziness 30% Itchy nose 4% Nausea 6% Dysphoria 4% Hallucinations 6%
Yeaman, 2013 Ketamine for analgesia (sub-dissociative low dose)	28	3-13 years	Emergency Department, Australia	Observational study: Ketamine	Ketamine 0.8-1.48 mg/kg	IN	IN ketamine provided adequate analgesia by 30 minutes. Median VAS decreased from 74.5 mm to 30 mm.	Dizziness 36% Bad taste 29% Dysphoria 14% Nausea 11% Sore throat 7% Diplopia 7% Amnesia 4% Headache 4% Vomiting 4%
Johansson, 2013 Ketamine for analgesia (sub-dissociative low dose)	9	7-36 years	Prehospital trauma, Sweden	Case series: (S)-Ketamine	Ketamine 0.45 mg/kg-1.25 mg/kg	IN	IN S-ketamine provided adequate analgesia. Median pain score decreased from 10 to 3 (on a 10 point scale).	Vertigo Unpleasant taste
Tsze, 2012 Ketamine for sedation	12	1-7 years	Emergency Department, USA	Randomized, prospective double blind trial: Ketamine (3 doses)	Ketamine #1 3 mg/kg Ketamine #2 6 mg/kg Ketamine #3	IN	Significantly higher proportion of successful sedations with 9 mg/kg dose than	Vomiting 8%

(dissociative dosing)					9 mg/kg		the other two doses.	
Gyanesh, 2013 Ketamine for sedation (dissociative dosing)	150	1-10 years	Radiology (MRI), India	Randomized double blind trial: Dexmedetomidine (DXM) vs Ketamine vs Normal saline	DXM 1 mcg/kg Ketamine 5 mg/kg Normal saline	IN	DXM and ketamine were equally effective as pre-medication. In 90.4% of DXM patients and 82.7% of ketamine patients, satisfaction with conditions for IV insertion. Total dose of propofol used was less in DXM and ketamine groups.	DXM: Bradycardia 4% Nausea/Emesis 4% Ketamine: Nausea/Emesis 10% Saline: Nausea/Emesis 6%

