Baseline and demographic characteristics will be summarized by standard descriptive summary statistics. This will include means and standard deviations for continuous variables expected to be normally distributed, such as age, vital signs, capnometry values, weight and VAS pain scores; proportions for categorical variables such as gender, race and injury location; and medians with ranges for variables expected to not be normally distributed, such as UMSS sedation scores. All continuous variables will be assessed for normality; parametric statistics will be used for normally distributed variables and non-parametric statistics will be used for non-normally distributed variables.

Efficacy Analysis

The primary analysis will include all subjects randomized based on the principle of intention to treat. If necessary, a per-protocol analysis will also be performed to assess efficacy of the treatments actually received. The primary efficacy endpoint will be the difference in mean pain scores between the ketamine group and the fentanyl group at 30 minutes after study intervention. This difference will be evaluated using the t-test.

Demographic and historical baseline information of the 2 study groups will be compared using t-tests (means), Mann-Whitney U (medians), and chi-square (proportions) tests. If there are any significant differences, linear regression will be performed to adjust for significantly different covariates.

For secondary outcomes, t-tests, or Mann-Whitney U where appropriate, will be used to evaluate differences in continuous outcomes (e.g. heart rate, blood pressure). Chi-square tests will be used to evaluate proportions in dichotomous outcomes (e.g. proportion with presence of specific adverse effects). Risk differences with 95% confidence intervals will be used to compare dichotomous outcomes such as the use of rescue analgesia and adverse events.

Safety Analysis

All subjects entered into the study will be included in the safety analysis. The frequencies of adverse events, including type, body system, severity and relationship to the study drug, will be summarized. We do not anticipate any serious adverse events. However, if one were to occur, it would be described in detail.

Adverse event incidence will be summarized along with the corresponding exact binomial 95% two-sided confidence intervals.

Test of Non-Inferiority

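### Hypotheses 2a and 2b predict non-significant differences in sedation and capnometry, but the planned difference tests, with no margin and no interval, cannot support a conclusion of similarity

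*Combined protocol and SAP*

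**What the plan says.** Section II gives the second objective as estimation and comparison: "The secondary objective is to define and compare the level of sedation associated with intranasal sub-dissociative ketamine (1.5 mg/kg) and intranasal fentanyl (2 mcg/kg"), measured by UMSS and capnometry. The hypotheses beneath it are worded differently. 2a reads: "There will be no significant difference in mean sedation scale scores between the intranasal ketamine group and the intranasal fentanyl group". 2b begins: "There will be no significant difference in the mean capnometry values of the two groups". It then makes a separate prediction about individual patients: "Patients in both groups will not experience hypopneic hypoventilation (decrease in capnometry value of ≥ 10 mm Hg").

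The analysis is in section VIII, Statistical Methods. Under Efficacy Analysis: "For secondary outcomes, t-tests, or Mann-Whitney U where appropriate, will be used to evaluate differences in continuous outcomes". UMSS and capnometry are not named there. Confidence intervals are planned for dichotomous outcomes (risk differences) and, under Safety Analysis, for adverse event incidence (exact binomial). None is planned for a between-arm difference in a continuous secondary outcome.

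UMSS is defined in section VIII as a five-level score from 0 to 4. Under Baseline Data the plan uses "medians with ranges for variables expected to not be normally distributed, such as UMSS sedation scores", and adds that "parametric statistics will be used for normally distributed variables and non-parametric statistics will be used for non-normally distributed variables".

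The only margin, SDs and power statement (section VI, Sample Size and Power Analysis) concern the VAS pain score.

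**The concern.** A hypothesis that predicts a non-significant difference is met when a test fails to reject. That can happen because the arms are alike or because the trial is small, and the p-value does not tell these apart. For pain the plan deals with this through a 10 mm margin and a non-inferiority test. For sedation and capnometry it offers no counterpart, so a non-significant difference test is the only criterion in the text against which 2a and the first sentence of 2b could be judged.

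Two narrower problems sit beside this. The second sentence of 2b predicts zero events, and a zero count in a sample of this size is weak evidence about the underlying rate. Hypothesis 2a concerns a mean, while section VIII points away from means for the same score.

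What is at stake is the trial's statement on its second objective. The Background presents an objective respiratory profile from capnometry as something earlier work lacks. A summary that sedation and ventilation did not differ, resting on p-values alone, would say more than the data can carry.

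**Working it through.** **Inputs from the documents.** 39 evaluable children per arm; 90 to be enrolled at 1:1, so 45 per arm; VAS margin 10; assumed true difference 5 in ketamine's favour (45 against 40); SDs 29.63 and 22.22; one-sided α 0.05; power 80%. No SD, margin or power is given for UMSS or capnometry, so those outcomes are treated in SD units or with stated assumptions.

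**1. The plan's own figure.** Common SD = √[(29.63² + 22.22²)/2] = 26.19. The distance from the assumed truth to the margin is 10 + 5 = 15. Normal approximation: n = 2 × (1.645 + 0.842)² × 26.19² / 15² = 37.7, so 38. With the noncentral t, power is 79.6% at 38 and 80.6% at 39. The stated 39 reproduces, but it relates to VAS only.

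**2. How often a real difference is non-significant.** Two-sided t-test at 0.05, n per arm, true difference d in SD units, noncentrality d/√(2/n):

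| n per arm | √(2/n) | d = 0.3: noncentrality, P(non-significant) | d = 0.5: noncentrality, P(non-significant) |
|---|---|---|---|
| 39 | 0.2265 | 1.32, 74% | 2.21, 41% |
| 45 | 0.2108 | 1.42, 71% | 2.37, 35% |

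These figures describe an outcome analysed by t-test, such as capnometry. They do not describe a rank test on UMSS.

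**3. What an interval would show.** The 95% half-width is t(0.975, 2n−2) × √(2/n): 1.992 × 0.2265 = 0.45 SD at 39 per arm and 1.987 × 0.2108 = 0.42 SD at 45. If the capnometry SD were anywhere from 3 to 10 mm Hg (an assumption), the half-width at 39 per arm would be 1.4 to 4.5 mm Hg.

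**4. Could this sample show similarity?** Power of two one-sided tests (α 0.05 each, true difference 0, 39 per arm) is about 0% for a margin of 0.3 SD, 42% for 0.5 SD and 85% for 0.7 SD. By the normal approximation n = 2 × [(1.645 + 1.282)/margin]², 80% power needs about 191, 69 and 35 per arm. The answer therefore turns on a margin that the plan does not set.

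**5. Zero hypoventilation events.** The exact two-sided 95% upper limit for 0/n is 1 − 0.025^(1/n), which gives 9.0% for n = 39 and 7.9% for n = 45, in each arm.

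**6. UMSS, with assumed distributions.** Suppose scores 0/1/2/3 occur in 35/50/13/2% of one arm and 30/40/25/5% of the other. Both medians are 1, while the share scoring 2 or more is 13 + 2 = 15% against 25 + 5 = 30%. By simulation, Mann-Whitney is non-significant about 79% of the time at 39 per arm and 76% at 45. Had those shares been observed at 39 per arm, the risk difference would be 15 points with a 95% half-width of 1.96 × √(0.15 × 0.85/39 + 0.30 × 0.70/39) = 18 points. The interval shows the uncertainty directly; the p-value alone does not.

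**The case against.** The strongest reply is that the plan nowhere says a p-value above 0.05 will be read as equality. The objective is to define and compare, and the tests are there to evaluate differences. Hypothesis 1 uses similar non-significance wording, yet that outcome receives a proper non-inferiority test, so hypothesis wording in this protocol does not settle the inference. This is correct as a reading of the text: equating non-significance with equality is something a reader might infer, not a stated decision rule. But the example of Hypothesis 1 also shows the gap. Pain has a later section that supplies the missing inference; UMSS and capnometry have none.

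A reader might also infer that the sample is too small to support similarity at all. The documents do not show that. With a margin of about 0.7 SD or wider, 39 per arm would be enough, and plausible capnometry intervals lie well inside 10 mm Hg, although that figure is a threshold for a patient and not a margin between groups.

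A third tempting reading is that UMSS is compared by medians, so that a shift in sedation with equal medians would go unseen. The median line is a descriptive summary under Baseline Data. The general rule leads to Mann-Whitney, which works on ranks and can detect such shifts: if 10% against 40% of children score 1 and the rest 0 (assumed), both medians are 0 and simulated power is about 90% at 39 per arm. That rule also largely settles which test applies, so the mismatch with the mean in 2a is mainly one of wording.

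Finally, a capnometry fall of 10 mm Hg or more is dichotomous, and section VIII already has suitable methods for dichotomous outcomes and adverse events. What is missing is an explicit statement that they apply to this outcome.

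**Conclusion.** The point stands in limited form. As planned, the analysis of UMSS and capnometry cannot support a conclusion of similarity, because it has difference tests only, no margin and no interval for the between-arm difference. The size of the problem for a t-tested outcome is a 74% chance of non-significance at a true 0.3 SD and 41% at 0.5 SD with 39 per arm (71% and 35% with 45), assuming normal outcomes with equal variances. Whether the sample itself could support similarity cannot be decided from the documents, since it depends on a margin and SD they do not give.

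The zero-event prediction in 2b cannot be generalised from a zero count: true rates up to 9.0% (39) or 7.9% (45) per arm would remain compatible with it. The mean in 2a does not fit the plan's own treatment of UMSS.

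All of this concerns secondary outcomes. The primary non-inferiority conclusion on pain is unaffected.

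**What to change.** - Restate 2a and 2b as estimation aims, in line with the stated objective.
- Report the between-arm difference in EtCO2 change from baseline with a two-sided 95% CI at each assessment.
- Replace the mean in 2a with UMSS proportions at pre-set cut-points (for example 1 or more, and 2 or more), with risk differences and 95% CIs.
- Name a capnometry fall of 10 mm Hg or more, the threshold in 2b, as a dichotomous outcome. State which readings count, report it per arm with an exact 95% CI, and apply the methods section VIII already holds for dichotomous outcomes and adverse events.
- State that p > 0.05 will not be reported as no difference. If a claim of similarity is wanted, set and justify a margin before unblinding.

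The cost is a few sentences in the plan and some intervals from data already being collected; no new patients, visits or measurements are needed. The price is a less emphatic claim about sedation and ventilation.
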